7.7. Follow-Up Contact (Day 0 + 35±2)

Participants will be contacted at Day 0 +35±2 to monitor overall status and record adverse events.

- (1) Follow-Up Phone Script
- (2) Gastrointestinal Symptom and Severity Checklist - symptom rating
- (3) Record adverse events as reported by subject

7.8. Premature Discontinuation

If a subject withdraws or the investigator discontinues subject participation after Visit 1, data from that visit will be included in the analysis of Objective 1, but not Objective 2

7.9. Collection and Management of Tissue Specimens

Sample Preparation:

Stool samples: After collection, samples should be immediately placed in the provided DNA/RNA Shield™ Fecal Collection Tube (Zymo Research Catalog No. R1101). The procedures for sample collection and stabilization should be carried out as quickly as possible. Samples can be stored at ambient temperature (4°C-25°C) for ≤ 2 years and frozen (< -20°C) indefinitely. In the Core facility, samples will be stored at -80°C until processed.

Blood samples: Samples will be collected on site using BD Vacutainer™ Venous Blood Collection Tubes: SST™ Serum Separation Tubes (FisherScientific Catalog No. 02-683-148) and stored at -80°C immediately after serum separation.

Record Keeping and Monitoring: The following procedures will be applied for maintaining sample accountability and traceability and for ensuring regulatory compliance.

1. Make sure the cryovial cap is secured tightly
2. Review the patient's Stool Sample Collection Log
3. Complete the cryovial labels

Patient #: _____

Visit # _____ and Date _____

Collection place: Home or Study Site

4. Affix a label on each cryovial and put in plastic bag. Store the cryovials immediately in the -80°C freezer.
5. Complete the stool sample tracking log (only if sample is kept)

Sample Storage and Security:

Study personnel will receive, assess for integrity and relevant information, and store stool samples mailed by participants. Blood samples will be collected on site (V1 and V2) and placed immediately in ice and stored at – 80°C. Stool and blood samples will be stored in the UNC Microbiome Core in a designated -80°C freezer (serial #: 0160203301161024, located in Taylor Hall, room 312C). Only study personnel will have access to the blood and stool samples. All samples will be stored at UNC MCF until the study is completed.

8. Study Measurements and Evaluations

8.1. Outcome Measures for Evaluation of Feasibility / Tolerability

Tolerability will be assessed and recorded by the following parameters:

- (1) Occurrence of drop-out
- (2) Adherence/compliance
- (3) Side effects (bloating, flatulence, belching, abdominal pain, discomfort, watery stool, and vomiting) will be monitored every week via text, email, or phone call using the PROMIS Gastrointestinal Symptom Scale.

8.2. Outcome Measures for Evaluation of Efficacy

N/A

8.3. Outcome Measures for Evaluation of Safety

The incidence and severity of AEs will be assessed during the study at visit 2 and every week via email, phone call, and/or text messages.

8.4. Other Outcomes in the Causal Pathway

N/A

8.5. Baseline Characteristics of the Participants

Apparently healthy adults 18-55 years old. All participants will be nonsmoking and well-nourished according to standard anthropometric criteria.

Enrollment will not be restricted based on race, ethnicity, or gender. Subject population will reflect the population in the long-term care facility providing a broad selection of individuals to allow to enroll subjects from all races, ethnicities and genders as represented in North Carolina state.

8.6. Variables Representing Treatment

A total of 45 individuals will be randomized 1:1:1 (placebo, GOS, hGOS) to treatment. Allowing for a 20% drop out rate, approximately 55 - 60 subjects will be enrolled.

9. Statistical Analysis Plans

a. Strategies that Apply to all the Specific Aims

- (1) To help ensure replicability of the research, the analysis plans will be reviewed and finalized prior to collection of data (a priori). For the specific aim, the analysis plan specifies detailed steps for obtaining estimates of population parameters (e.g intervention safety) and for making inferences.
- (2) Sensitivity analyses will be performed to assess the robustness of the major results as indicated by their sensitivity to reasonable perturbations of the choices of the methods and assumptions used. Any question about the optimal choice of methods and assumptions are best handled by relegating competing approaches to roles in the domain of sensitivity analyses. Results of the sensitivity analyses will be used to guide our level of trust in the main results. Best practices for dealing with incomplete data will depend on the documented causes of missing, censored, and coarsened values. The reasons for missing data values, drop-out, and protocol departures will have been documented in/with the database.
- (3) The plan also includes outcome-dependent exploratory analyses to generate new hypotheses.
- (4) Descriptive graphical and tabular methods will be used to characterize the participants, visualize the data, and examine relationships among variables.
- (5) To indicate precision, all statistical estimates of population parameters will be tabulated along with corresponding confidence intervals (CI) or standard errors (SE). The CI will be interpreted as the set of potential values of the population parameter that are most compatible with the observed data.
- (6) All hypothesis tests yielding p-values that are deemed to be not statistically significant will be reported as being inconclusive. The proposed statistical analysis strategy acknowledges that no p-value can reveal the plausibility, presence, truth, or importance of an association or effect-- which is consistent with the statements of the American Statistical Association [4,5], the recommendations in Nature [6,7], and guidance, such as the CONSORT Statement [1], STROBE Statement [2], and ICMJE guidance [3].²

9.1. Description of the Study Cohort

A table will be used to summarize the participant cohort characteristics (age, gender) as well as basic dietary information. Figures will be used to feature microbiome analysis data and inflammatory biomarkers.

9.2. Aim-Specific Plans

Plans for Aim 1 (A1): Validate 15 g/day dose safety and tolerability (absence of GI adverse effects) of GOS and hGOS in healthy adults.

Method. We will report descriptive statistics for demographics, basic medical history, prescription and over the counter, and dietary supplements, including means and standard deviations for continuous variables, and percentages and ranges for categorical data. We will report the number and percent of all individuals (intent to treat) who had any adverse event (prompted or in response to an open-ended question). We will also report the number and percent of events over time, as well as the severity of the event.

Statistical analysis for A1. Data will be presented as mean \pm SD for variables that are normally distributed, or median (IQR) for variables not normally distributed. Binary/categorical outcomes will be reported as a percentage with confidence interval.

Plans for Aim 2: Establish a biological signature of GOS and hGOS through assessment of prebiotics effects vs placebo on:

(A2.1) Abundance of beneficial gut bacteria and restoration of the gut microbiome saccharolytic potential

Method. Determination of abundance of beneficial bacteria (*Bifidobacterium* and *Akkermansia* species) in the gut microbiome of treatment and placebo groups and the microbiome saccharolytic potential by Whole Genome Shotgun (WGS) sequencing⁵⁵. For assignment of saccharolytic (SAC) and non-saccharolytic (NON_SAC) phenotypes we will use the reference study by Vieira-Silva *et al.*²⁶ as described⁹.

Statistical analysis (A2.1). we will perform both exploratory analysis and statistical testing for changes in plasma cytokines. Data will be presented as mean \pm SD. To find the change of microbiome abundance under difference circumstance, Mann-Whitney-Wilcoxon matched pair tests between baseline and 4 weeks follow-up will be performed for abundance of beneficial gut bacteria in each treatment arm. To compare the change of microbiome abundance in three arms, we will apply the Kruskal-Wallis test whether the change of microbiome abundance is the same among three groups. Due to multiple testing was proposed in A2.1, p values will be corrected for the total number of comparisons with a controlled false-discovery rate (FDR)

ditching statistical significance: Looking beyond a much used and abused measure would make science harder, but better. *Nature* 567, 283-283.

(A2.2) Modulation of biomarkers of inflammation

Rationale. High-sensitivity C-reactive protein (hs-CRP) is a recognized marker of systemic inflammation³⁴ and specific pro-inflammatory cytokines mediate interaction between immune cells and non-immune cells, contributing to the inflammatory status of the intestine^{35, 36}. Based on previous studies with probiotics and prebiotics that report potential immunomodulatory effects³⁷⁻³⁹, we decided to monitor hs-CRP, IL-1 α , IL-1 β , IL-2, IL-6, IL-8, IL-12, TNF α , and IFN γ for the duration of the clinical trial.

Method. Determination of levels of biomarkers of inflammation (IL-1 α , IL-1 β , IL-2, IL-6, IL-8, IL-12, TNF α , and IFN γ) as well as high-sensitivity C-reactive protein, a marker of low-grade inflammation (hsCRP) in serum. We will determine cytokine levels using the MCYTOMAG-70K (Milliplex) in the Advanced Analytics Core (AAC) of the CGIBD. hsCRP concentration will be measured via hsCRP ELISA (Sigma Aldrich).

Statistical analysis (A2.2). Similar to A2.1, we will perform an exploratory analysis of changes in plasma cytokines. Data will be presented as mean \pm SD. To find the change of biomarker of interest under difference circumstance, paired t-test for matched pair between baseline and 4 weeks follow-up will be performed for levels of biomarkers in each treatment arm. To compare the change of biomarker level in three arms, we will use ANOVA to test whether the change of biomarker level is the same among three groups. Due to multiple testing, p values will be corrected for the total number of comparisons with a controlled false-discovery rate (FDR)

(A2.3) Evaluation of intestinal barrier function.

Method. Blood samples will be drawn and serum will be used to quantify zonulin using the Zonulin (IDK® Zonulin) (Serum) ELISA test (Immundiagnostik AG). Zonulin is a biomarker of impaired intestinal permeability, which has been associated with various disorders^{56, 57}.

Statistical analysis (A2.3). Since A2.3 has similar data and analytic goal as A2.2, the analytic approach will be the same as what we proposed in A2.2.

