¹ [1] www.consort-statement.org [2] www.strobe-statement.org [3] www.icmje.org [4] Wasserstein RL, et al. (2016), The ASA's Statement on p-Values, *The American Statistician*, 70:2, 129-133 [5] Wasserstein RL, et al. (2019), Moving to a World Beyond $p < 0.05$, *The American Statistician*, 73:sup1, 1-19 [6] Amrhein, et al. (2019) Scientists rise up against statistical significance, *Nature* 567, 305-307 [7] Editorial (2019) It's time to talk about ditching statistical significance: Looking beyond a much used and abused measure would make science harder, but better. *Nature* 567, 283-283.

Abbreviations and Definitions of Terms

Abbreviation/Acronym	Definition
AE	Adverse Event/Adverse Experience
CI	Confidence Interval
CRC	Colorectal Cancer
CRF	Case Report Form
CRP	C-Reactive Protein
eCRF	Electronic Case Report Form
FDA	Food and Drug Administration
GCP	Good Clinical Practice
GI	Gastrointestinal
GOS	Galacto-oligosaccharides
Gal	Galactose
Glc	Glucose
GSSC	Gastrointestinal Symptom and Severity Checklist
hGOS	GOS enriched with LacNAc; humanized GOS
HIPAA	Health Insurance Portability and Accountability Act
IB	Investigator's Brochure
IBD	Inflammatory Bowel Disease
IBS	Irritable Bowel Syndrome
ICF	Informed Consent Form
IL	Interleukin
INF	Interferon
IND	Investigational New Drug Application
IRB	Institutional Review Board
N	Number (typically refers to subjects)
NDA	New Drug Application
PI	Principal Investigator
QA	Quality Assurance
QC	Quality Control
SAE	Serious Adverse Event/Serious Adverse Experience
SD	Standard Deviation
SE	Standard Error
SOP	Standard Operating Procedures
TNF	Tumor Necrosis Factor
UC	Ulcerative Colitis
UP	Unanticipated Problem
WGS	Whole Genome Shotgun (Sequencing)

1. Protocol Synopsis

Study Title	Safety, Tolerability, and Biosignature of Humanized Prebiotics in Healthy Adults
Objectives	
Objective 1. Validate 15 g/day dose safety and tolerability (including absence of GI adverse effects) of GOS and hGOS in healthy adults.
 
Objective 2. Establish a biological signature of GOS and hGOS through assessment of prebiotics effects vs placebo (powdered corn syrup comprised of fructose, glucose, and an inert cellulose material that matched the consistency, color, sweetness, and taste of the prebiotics) on (i) abundance of beneficial gut bacteria and restoration of the gut microbiome saccharolytic potential, (ii) modulation of biomarkers of inflammation and (iii) evaluation of intestinal barrier function.

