- (2) Determination of levels of biomarkers of inflammation (IL-1 α , IL-1 β , IL-2, IL-6, IL-8, IL-12, TNF α , and IFNy) as well as high-sensitivity C-reactive protein, a marker of low-grade inflammation (hsCRP) in serum. We will determine cytokine levels using the MCYTOMAG-70K (Milliplex) in the Advanced Analytics Core (AAC) of the CGIBD. (ii) hsCRP concentration will be measured via hsCRP ELISA (Sigma Aldrich).

Measurements in stool:

Determination of abundance of beneficial bacteria (*Bifidobacterium* and *Akkermansia* species) in the gut microbiome of treatment and placebo groups and the microbiome saccharolytic potential using WGS sequencing, the most accessible, cost-effective measure currently available.

4.4.Outcome Measures

Primary Outcome(s):

The expected outcome is to confirm a 15 g/day as a safe and tolerable dose of GOS and hGOS in healthy adult individuals using the 38-point Gastrointestinal Symptom and Severity Checklist (GSSC).

Secondary Outcome(s):

Definition of prebiotic biosignature characterized by:

- Increased abundance of saccharolytic bacteria (*Bifidobacterium*) and other beneficial bacteria (*Akkermansia*)
- Modulation of biomarkers of inflammation
- Improved intestinal barrier function.

Tertiary/Exploratory Outcome(s): N/A

Other Measures: Baseline Characteristics and Assigned Treatments: N/A

5. Study Participants

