10.1. Risk / Benefit Assessment

Potential Risks: Subjects in the GOS and hGOS groups will consume 7.5-15g/day of the prebiotics or placebo preparations as a drink. Possible side effects of the GOS and hGOS groups may include mild to moderate bloating, gas (flatulence), belching, abdominal pain or discomfort, and vomiting. Individuals will be withdrawn from the study if treatment leads to severe side effects.

Potential Benefits: Substances defined as "prebiotics" (a substrate that is selectively utilized by host microorganisms conferring a health benefit per the latest definition of the International Scientific Association for Probiotics and Prebiotics, ISAPP) have a demonstrated beneficial effect in humans and animals. Galacto-oligosaccharides (GOS) in particular have been shown to alleviate symptoms of lactose intolerance and other minor gastrointestinal manifestations in adequate doses.

A compromised gut barrier, dysbiosis and inflammation are hallmarks of the aging gut with consequences that can range from mild GI manifestations like constipation, abdominal pain, and flatulence, to disorders of the gut-brain axis and other conditions not directly associated with the GI tract. This study will add to the knowledge of beneficial modulation of the microbiota to mediate restoration of the gut barrier and biomarkers of inflammation. A positive outcome from

this study will further advance research to improve nutritional conditions and overall health of older individuals in long-term care.

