- (3) Temporal relationship – Is there a reasonable temporal relationship between the time of onset of the event and the administration of the investigational product?
- (4) Concomitant medication – Is the event a known side effect of a concomitant medication?

Based on the previous factors we will consider the following descriptions when assessing relationship of an event to the investigational product:

Definite: There is a reasonable causal relationship between the investigational product and the AE, when the event responds to withdrawal of the investigational product (de-challenge) and recurs with re-challenge by administration of the investigational product.

Probable: There is a reasonable causal relationship between the investigational product and the AE. The event responds to de-challenge. Re-challenge not required.

Possible: There is a reasonable causal relationship between the investigational product and the AE. De-challenge is lacking or unclear.

Not Likely: There is a temporal relationship between the investigational product administration and the AE, but there is not a reasonable causal relationship between investigational product and the event.

Unrelated: There is not a temporal or causal relationship to the investigational product administration.

The Investigator will record causal relationship in the source documents, as appropriate, and report such an assessment in accordance with the SAE reporting requirements, if applicable.

Expectedness Definition: An assessment of expectedness will be performed for each AE and SAE. Previously reported expected effects of prebiotic administration include abdominal pain (cramps), bloating, flatulence (gas) and diarrhea (loose stools >3 times/day). During the study, GI side effects will be expected and only AEs that are meet the definition of severe AE or considered an SAE will be reported to the IRB or FDA.

AE and SAE Assessment, Follow-up Procedures: The Investigator will record all directly observed AEs and all AEs spontaneously reported by the study subject beginning from the time the subject begins use of the investigational product through 7 days after the last dose of the investigational product. Changes in health status after the subject has provided informed consent but before the subject begins use of the investigational product shall be recorded as changes in the medical history.

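### Aim 1 claims more than about 16 per arm can show: it should estimate GI events by arm and their difference from placebo, not validate their absence

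*Combined protocol and SAP*

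**What the plan says.** Aim 1 is worded in five places.

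- Section 9.2, plans for Aim 1: "Validate 15 g/day dose safety and tolerability (absence of GI adverse effects) of GOS and hGOS in healthy adults".
- Synopsis, Objective 1: the same verb, with the parenthesis "including absence of GI adverse effects".
- Sections 2.1 and 3.1: the same verb, without the parenthesis.
- Section 4.4, primary outcome: "The expected outcome is to confirm a 15 g/day as a safe and tolerable dose of GOS and hGOS in healthy adult individuals".

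None of these gives an acceptable rate, a margin or a decision rule.

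On GI effects, section 10.1 says "Possible side effects of the GOS and hGOS groups may include mild to moderate bloating, gas (flatulence), belching, abdominal pain or discomfort, and vomiting". Under the expectedness definition, section 10.3 says "Previously reported expected effects of prebiotic administration include abdominal pain (cramps), bloating, flatulence (gas) and diarrhea (loose stools >3 times/day", and then "During the study, GI side effects will be expected".

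The Aim 1 analysis in 9.2 reports the number and percent of all individuals (intent to treat) with any adverse event, events over time, severity, and percentages with a confidence interval. It does not say that these are by arm, and it names no comparison with placebo. Aim 2, in the same section, is framed as an effect versus placebo. The statistical paragraph of the synopsis assigns chi-square or Fisher tests to incidence data but names no endpoint and no pair of groups. Section 9.5 says that the sample size for tolerability did not come from a power analysis.

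**The concern.** The primary aim promises a conclusion that the planned analysis cannot deliver. A small arm with few or no GI events does not establish absence, and the plan gives no criterion by which the dose would count as validated.

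A percentage within an arm also cannot be attributed to the product. Section 5.2 excludes only baseline responses of 4 or 5 on the listed symptom items, so participants may enter with lower-level bloating, pain or discomfort. The placebo arm is the means of separating background symptoms from product effects, and the Aim 1 plan does not use it to produce an estimate. What is at stake is what the trial can conclude on its primary aim. Data collection is not affected.

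**Working it through.** **1. The plan's own figure.** Section 9.5: 60 recruited, 20% dropout. 60 × (1 − 0.20) = 48, and 48 / 3 = 16 per arm. This reproduces. No power or precision figure is given for tolerability.

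**2. Other arm sizes the document allows.** Section 8.6: 45 randomised, 45 / 3 = 15. Synopsis and section 5.1: 48 enrolled; with 20% dropout, 48 × 0.8 / 3 = 12.8, about 13. If all 60 in section 9.5 are randomised and analysed by intent to treat, 60 / 3 = 20.

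**3. What zero events would show.** Section 9.2 states neither the confidence level nor the method; 95% and the exact binomial limit are assumed. With 0 events in n, the two-sided upper limit is 1 − 0.025^(1/n) and the one-sided limit is 1 − 0.05^(1/n).

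| n | two-sided 95% | one-sided 95% |
|---|---|---|
| 13 | 24.7% | 20.6% |
| 15 | 21.8% | 18.1% |
| 16 | 20.6% | 17.1% |
| 20 | 16.8% | 13.9% |
| 32 (two prebiotic arms of 16 pooled) | 10.9% | 8.9% |

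**4. How often an arm of 16 would show no event.** The documents give no GI event rate, so true rates p are assumed. The chance is (1 − p)^16: 44% at p = 5%, 19% at 10%, 2.8% at 20%, 0.3% at 30%. A clean arm is quite possible at rates of 5% to 10%, and unlikely at 20% or more.

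**5. What a placebo contrast would look like.** The counts are illustrative only: 4/16 on a prebiotic, 2/16 on placebo.

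- Wilson 95% limits: 10.2% to 49.5% for 4/16, and 3.5% to 36.0% for 2/16.
- Difference: 25.0 − 12.5 = 12.5 points.
- Newcombe lower limit: 12.5 − √[(25.0 − 10.2)² + (36.0 − 12.5)²] = 12.5 − 27.8 = −15.3.
- Newcombe upper limit: 12.5 + √[(49.5 − 25.0)² + (12.5 − 3.5)²] = 12.5 + 26.1 = 38.6.
- Fisher's exact test on the same counts: p = 0.65.

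The interval shows what the data leave open, from 15 points fewer to 39 points more. The p-value alone does not.

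**The case against.** The strongest reply is that this is a labelled pilot with a descriptive Aim 1. Section 9.5 is open about the lack of a power basis. Section 9, part a, item 5 requires intervals or standard errors with all estimates, and item 6 treats non-significant tests as inconclusive, so a 0/16 result would be reported with its uncertainty. All of that stands. It means the fault lies in the claim and the missing contrast, not in the sample size.

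Three stronger readings are tempting, and the documents do not support them.

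- *A reader might infer that any single GI symptom refutes the aim.* The absence gloss appears only in the synopsis and 9.2. Sections 2.1, 3.1 and 4.4 omit it. Sections 4.3 and 8.1 describe tolerability through frequency and severity of side effects, drop-out and adherence. Nothing makes one symptom a failure.
- *A reader might infer that section 10.3 flatly contradicts the aim.* Its statement belongs to a classification that decides what is reported to the IRB or FDA, and it predicts no rate. Section 10.1 speaks of possible effects. An aim can hope for few events while classing them as expected. The tension is real, but it is one of wording.
- *A reader might infer that no group comparison of GI events is planned anywhere.* The synopsis does assign chi-square or Fisher tests to incidence data. But that line names no endpoint, is not carried into 9.2, and yields only a p-value.

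**Conclusion.** The point holds as a fault in the claim and in the Aim 1 analysis. With 16 per arm, zero GI events leave true rates up to 20.6% compatible with the data (two-sided 95%, exact). No arm size the document supports brings that below 16.8%. Neither *validate* nor *confirm* can be earned, and absence cannot be shown. Section 9.2 does not commit to by-arm results or to an estimated difference from placebo, which is the quantity needed to attribute symptoms to the product.

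The bounds rest on a 95% level and exact limits, which the plan does not specify. The event probabilities rest on assumed rates, and the 4/16 versus 2/16 example is an illustration, not a forecast. The wording and analysis should be changed; nothing here calls for more participants.

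**What to change.** 1. Delete the absence gloss in the synopsis and section 9.2.
2. Replace *validate* or *confirm* with *estimate* in the synopsis and sections 2.1, 3.1, 4.4 and 9.2.
3. In 9.2, report by arm, in all randomised participants, the proportion with a GI event the protocol already defines: a 2-level increase from baseline on the PROMIS items listed in section 6.7. Give the difference of each prebiotic from placebo with a 95% interval, for example Newcombe. This follows section 9, part a, item 5.
4. Reconcile the synopsis line on chi-square and Fisher tests with 9.2, naming the endpoint and comparison if the tests are kept.
5. State the precision at the planned arm size: for example, that 0/16 leaves rates up to 20.6% open. This requires settling which total N applies.
6. Do not make dose reduction part of the endpoint yet. Sections 6.7, 10.2 and 10.4 describe it differently, and the investigators must reconcile them first.

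The cost is edited wording in five places and one interval per prebiotic, from data already collected. The downside is a less favourable claim for the primary aim.

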9.5. Sample Size Rationale

Tolerability: The sample size for tolerability was not determined from power analysis but based on multiple previous clinical trials conducted with GOS⁵⁸⁻⁶¹.

Microbiome: Our previous studies^{10, 11, 31, 32} conducted with a different but equivalent GOS preparation (purified prebiotics) have demonstrated a consistent and statistically significant increased abundance of the targeted beneficial bacteria: *Bifidobacterium* and *Akkermansia*. The proposed pilot study will recruit

60 subjects. After estimated dropout rate of 20%, the final subjects that will complete the subject will be N=48, which is 16 for each arm. This sample size is chosen given limited funds available with the pilot award supporting this project.

Biomarkers of inflammation: Since this is the first study, we do not have the estimate of effect size so the power cannot be computed. Additionally, due to the limitation of the funding with n=20, we do not expect to have sufficient power to detect differences over time. In that case, we will perform an exploratory analysis of changes in plasma cytokines and biomarkers of inflammation and compare the summary statistics such as mean and standard error.

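### Aim 1 is worded to validate or confirm 15 g/day as safe and tolerable, but its descriptive analysis sets no acceptable rate and no contrast with placebo, so it can only estimate.

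*Combined protocol and SAP*

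**What the plan says.** Section 9.2 gives Aim 1 as "Validate 15 g/day dose safety and tolerability (absence of GI adverse effects) of GOS and hGOS in healthy adults". Objective 1 in the synopsis carries the same parenthesis with the word *including* in front, so absence is there one component of tolerability. Section 3.1 states the aim without the parenthesis. The primary outcome in 4.4 reads "The expected outcome is to confirm a 15 g/day as a safe and tolerable dose of GOS and hGOS in healthy adult individuals", judged with the symptom checklist and without a cut-off.

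The Aim 1 analysis in 9.2 is descriptive. It gives the number and percent with any adverse event, prompted or volunteered, by intention to treat, with events over time and severity. On inference it says only "Binary/categorical outcomes will be reported as a percentage with confidence interval". It names no confidence level, acceptable rate, margin or comparison with placebo. The synopsis lists chi-square or Fisher tests for incidence data but does not tie them to Aim 1. On testing in general, 9.a item (6) says "All hypothesis tests yielding p-values that are deemed to be not statistically significant will be reported as being inconclusive".

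Section 10.3 says "During the study, GI side effects will be expected", and 10.1 lists bloating, gas and abdominal pain among possible effects.

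On numbers, 9.5 says "After estimated dropout rate of 20%, the final subjects that will complete the subject will be N=48, which is 16 for each arm" and adds that the size for tolerability did not come from a power analysis. Section 8.6 says "A total of 45 individuals will be randomized 1:1:1 (placebo, GOS, hGOS) to treatment".

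**The concern.** The primary aim promises a conclusion, that a dose has been validated, and the plan contains no analysis that could deliver it.

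The only phrase that says what a validated dose would look like is absence of GI effects. That sits badly with 10.3, which expects such effects. A percentage for each arm does not separate the product from the symptoms healthy adults report anyway when asked every week. A non-significant comparison with placebo, if one were run, would be inconclusive by the plan's own rule.

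What is at stake is the headline. If the wording stays, *confirmed safe and tolerable* would rest on a reading chosen after the data are seen, in arms too small to exclude a substantial event rate.

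**Working it through.** **Inputs.** Arm size: 16 (9.5), with 15 from 45 randomized 1:1:1 (8.6) and 20 if all 60 recruited are randomized and analysed by intention to treat (9.2, 9.5). Confidence level: not stated, so two-sided 95% is assumed. Background rate of GI events: not stated, so a range is assumed.

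**1. The plan's own figure.** 60 × (1 − 0.20) = 48, and 48 / 3 = 16 per arm. It reproduces.

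**2. What zero events would show.** The exact (Clopper-Pearson) two-sided 95% upper bound for 0 of n is 1 − 0.025^(1/n).

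| n per arm | Upper bound |
|---|---|
| 15 | 21.8% |
| 16 | 20.6% |
| 20 | 16.8% |

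A one-sided 95% bound for n = 16 is 1 − 0.05^(1/16) = 17.1%. A true rate of 10% gives 0 of 16 with probability 0.9^16 = 18.5%.

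**3. What a literal absence standard would do to an inert product.** The chance of at least one event among m people at background rate p is 1 − (1 − p)^m. Aim 1 covers both prebiotics, so m = 32; one arm (m = 16) is shown for comparison.

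| Assumed p per person | One arm, m = 16 | Both arms, m = 32 |
|---|---|---|
| 2% | 28% | 48% |
| 5% | 56% | 81% |
| 10% | 81% | 97% |

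A 95% chance of failing needs p of about 9% with 32 people (1 − 0.05^(1/32) = 8.9%), or 17% with 16.

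**4. What a difference from placebo could show.** The Newcombe 95% interval combines the Wilson limits l and u of the two arms. With equal proportions p its half-width is √[(p − l)² + (u − p)²]. For 3 of 16 in each arm, p = 0.1875, l = 0.066 and u = 0.430, so the half-width is √(0.122² + 0.243²) = 0.271.

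| Affected per arm of 16 | Half-width, percentage points |
|---|---|
| 2 v 2 | 25.2 |
| 3 v 3 | 27.1 |
| 4 v 4 | 28.6 |

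Identical incidence of 3 of 16 in both arms would thus exclude only an excess above about 27 points.

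**The case against.** The strongest reply is that the protocol contains no rule by which a single GI event fails the dose. The phrase in 9.2 is a parenthesis, the synopsis softens it, and 3.1 and 4.4 do not have it. Sections 4.3 and 8.1 judge tolerability on severity or frequency of side effects, drop-out and adherence. Section 10.3 assesses relatedness separately, so a background symptom is not automatically an adverse effect of the product. Eligibility excludes people with high scores on eight symptom items, and 10.4 uses change from baseline; both could keep background events low. Section 9.2 already promises percentages with intervals, and 9.a item (5) asks for an interval or standard error with every estimate, so 0 of 16 would be shown with its uncertainty. This is a pilot that admits it was not sized by power.

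Most of this stands. It disposes of the reading that absence is a formal pass/fail criterion. It does not supply what is missing. Severity, drop-out and adherence are listed without any level that would count as tolerable. An interval around one arm's percentage says nothing about excess over placebo. The pause rule at 5 of the first 20 (10.2, 10.4) and the termination rule at more than 20% with severe events (10.5) are safety triggers, not standards for a validated dose. If the parenthesis is not the standard, there is none, and the words *validate* and *confirm* are still unsupported.

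**Conclusion.** The point holds as a mismatch between claim and analysis. Aim 1 promises validation, 9.2 and 10.3 disagree on whether GI effects are to be absent or expected, and the planned analysis can yield only percentages or an inconclusive test. Zero events in an arm would be compatible with a true rate of up to 20.6% (n = 16, exact two-sided 95%), or between 16.8% and 21.8% across the arm sizes the documents imply.

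A reader might go further and infer that an inert product would almost always fail. The documents do not support that. It needs a background rate of about 9% per person across 32 people, or 17% in one arm, and no rate is given. The rate could be lower under the 2-level change in 10.4, and the failure figures apply only if any background event counts as an adverse effect. Nor do the documents support saying that the results could not tell a tolerable dose from an intolerable one: severity, drop-out and adherence are all reported. The defect is the absence of a stated basis for the conclusion, and it is cheap to repair.

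**What to change.** 1. Remove the absence parenthesis from Objective 1 in the synopsis and from Aim 1 in 9.2, so that both agree with 10.3.
2. Change *validate* and *confirm* to *estimate* in the synopsis, 3.1, 4.4 and 9.2, and in the matching sentence of 2.1.
3. In 9.2, report for GOS and for hGOS the difference from placebo in the proportion with a GI event, with a 95% interval. Use an event definition the protocol already has. The 2-level PROMIS change in 10.4 is one candidate, counted as a worsening, as 6.7 has it, with severity grades shown alongside. If it is chosen, 4.4, which names the GSSC, must be brought into line. The intention-to-treat denominator in 9.2 can stay.
4. State that the conclusion is limited to the excess over placebo that the upper limit excludes, and that neither zero events nor a non-significant test will be read as showing safety.
5. Give the expected precision in 9.5: a half-width of about 25 to 29 percentage points with 2 to 4 of 16 affected in each arm, and an upper bound of 20.6% for 0 of 16. Recompute both if the arm size is settled at another figure.

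This needs wording and one added comparison, using data already to be collected. No participants or visits are added. The downside is a less favourable headline, an estimate with wide limits in place of a confirmed dose.
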